2. SUMMARY OF KEY PROTOCOL INFORMATION

2.1. Changes to the Protocol Defined Statistical Analysis Plan

There were no changes or deviations to the originally planned statistical analysis specified in the protocol [Dated: 11/APR/2017].

2.2. Study Objective(s) and Endpoint(s)

Objectives	Endpoints

Part 1
 
• To assess the safety, tolerability and PK following single doses of GSK1325756H 10, 50 and 100 mg in the fed state in healthy Japanese subjects of over 65 years of age inclusive. 
Part 2
 
• To investigate the safety, tolerability and food effect on PK of GSK1325756 following a single dose of 50 mg in the fed and fasted state, in healthy Japanese subjects of over 65 years of age inclusive.	
Part 1 and Part 2
 
• Adverse events (AEs)• Change from baseline of clinical laboratory values, vital signs, and electrocardiogram (ECG) parameters• Blood concentration of GSK1325756• Cmax, AUC(0-t), AUC(0-inf), AUC(0-24), tmax, t1/2, tlag, tlast of the blood concentration of GSK1325756, as data permit

2.3. Study Design

Overview of Study Design and Key Features																														
Subjects will be divided into Part 1 and 2, and receive the following study treatment doses shown in Table below.																														
Part 1:																														

  
 Group	n	Period 1	Washout	Period 2	Washout	Period 3	
   
 A	6	10 mg	at least 7 days	50 mg	at least 7 days	Placebo	
 
 B	6	10 mg	Placebo	100 mg	
 
 C	6	Placebo	50 mg	100 mg	
  
							Group	n	Period 1	Washout	Period 2	Washout	Period 3	A	6	10 mg	at least 7 days	50 mg	at least 7 days	Placebo	B	6	10 mg	Placebo	100 mg	C	6	Placebo	50 mg	100 mg
Group	n	Period 1	Washout	Period 2	Washout	Period 3																								
A	6	10 mg	at least 7 days	50 mg	at least 7 days	Placebo																								
B	6	10 mg		Placebo		100 mg																								
C	6	Placebo		50 mg		100 mg																								
Part 2:																														

  
 Group	n	Period 1	Washout	Period 2	
   
 D	8	50 mg, fed	at least 7 days	50 mg, fasted	
 
 E	8	50 mg, fasted	50 mg, fed	
  
							Group	n	Period 1	Washout	Period 2	D	8	50 mg, fed	at least 7 days	50 mg, fasted	E	8	50 mg, fasted	50 mg, fed										
Group	n	Period 1	Washout	Period 2																										
D	8	50 mg, fed	at least 7 days	50 mg, fasted																										
E	8	50 mg, fasted		50 mg, fed																										
Design Features	
Part 1: This is a double blind, placebo-controlled, 3-period crossover, ascending dose, single oral administration in the fed condition.
 
Part 2: This is an open label, 2-way crossover, single oral dose in the fed and fasted state study.
																													
Dosing	
Part 1:
 
Subjects will have a screening visit within 30 days prior to the first dose of study. A minimum washout period of 7 days will be required between each treatment period. Subjects will receive three treatment periods in the study. Subjects will be housed in the Clinical Research Unit from Day -1 (the day before dosing) through Day 3 for Period 1 and 2, and from Day -1 (the day before dosing) through Day 4 for Period 3. Subjects will return to the clinic 7 days (at least) after the previous administration day for Period 1 and 2, and subjects will visit the unit on Day 8 (+/- 1 day) of the last dosing for Period 3 for follow-up.
 
Part 2:
 
Subjects will have a screening visit within 30 days prior to the first dose of study treatment, two treatment periods separated by at least 7 days, and follow-up. Subjects will be housed in the Clinical Research Unit from Day -1 (the day before dosing) through Day 3 (for Period 1 and 2), and re-visit 7 (± 1) days after the last dose of Period 2 for follow-up.
																													

Overview of Study Design and Key Features	
Treatment Assignment	
 • Sufficient participants will be randomised such that approximately 18 in Part 1 and 16 in Part 2 evaluable participants complete the study of each part. • If participants prematurely discontinue the study, additional participants may be enrolled as replacement participants and assigned to the same treatment sequence, if applicable, at the discretion of the sponsor in consultation with the investigator. • On Day 1 of each Part, participants will be assigned a unique number (randomization number) in ascending numerical order. The randomization number encodes the participant's assignment to one of the 3 sequences in Part 1 and one of the 2 sequences in Part 2, according to the randomization schedule generated prior to the study by the Biomedical Data Sciences Department at GSK. • Participants will be randomized in a 1:1:1 ratio to receive sequence (A:B:C) for Part 1, or will be randomized in a 1:1 ratio to receive sequence (D:E) for Part 2. • Each participant will be dispensed blinded study treatment, labeled with his unique randomization number, throughout the study. • Investigators, participants and sponsor will remain blinded to each participant's assigned study treatment throughout the course of the study. For the concentration evaluation after Period 2 of Part 1, the pre-specified sponsor's person who is responsible for the confirmation of the concentration will review blood drug concentration data under unblended.
Interim Analysis	
 • No formal statistical analysis is planned. • A blind review of preliminary safety data (AE, clinical laboratory values, vital signs, ECG) and blood concentration will be conducted between Period 2 and Period 3 in Part 1 and prior to Part 2. • After completion of Part 1, formal analysis for Part 1 is to be conducted.

2.4. Statistical Hypotheses

The objectives of this study are to evaluate safety, tolerability and PK profile of single dose of GSK1325756H and to investigate food effect of PK profile of single dose of GSK1325756H in healthy Japanese elderly subjects. No formal statistical hypotheses will be tested in Part 1 and Part 2. Descriptive statistics will be used to assess safety and tolerability objectives. An estimation approach will be used to address the PK study objectives, where point estimates and corresponding 95% confidence intervals will be constructed, unless otherwise stated.

3. PLANNED ANALYSES

3.1. Interim Analyses

No formal statistical analysis is planned. However, following Period 1 and Period 2 of Part 1, a blind review of preliminary safety data (AE, clinical laboratory values, vital signs, ECGs) will be conducted between Period 2 and Period 3 in Part 1 and prior to Part 2. Furthermore, the sponsor's person who is responsible for the confirmation of the concentration will review blood drug concentration data under unblended.

3.2. Final Analyses

The final planned primary analyses will be performed after the completion of the following sequential steps:

1. All subjects in each part have completed the study as defined in the protocol.
2. All required database cleaning activities in each part have been completed and final database release and database freeze has been declared by Data Management for each part.
3. All criteria for unblinding the randomisation codes have been met for Part 1.
4. Randomisation codes have been distributed according to RandAll NG procedures.

After completion of Part 1, formal analysis for Part 1 is to be conducted.

4. ANALYSIS POPULATIONS

Population	Definition / Criteria	Endpoint(s) Evaluated
Screened	
 • Consisting of all subjects screened in the study. 
Note: This definition indicates the same meaning as 'All subjects who have subject number' in a programming point of view.
	
 • Study Population
Screening Failure	
 • Subjects who screened in the study but are never subsequently randomized. All participants who sign the ICF have the screening test in the study. 
Note: This definition indicates the same meaning as 'Subjects who have subject number but are never subsequently randomized' in a programming point of view.
	
 • Study Population
Safety	
 • All randomized subjects who take at least one dose of study treatment. Participants will be analyzed according to the treatment they actually received. 	
 • Study Population • Safety

Population	Definition / Criteria	Endpoint(s) Evaluated
Pharmacokinetic	
 This population is defined as all subjects administered at least one dose of study treatment and who have PK sample taken and analysed. Participants will be analyzed according to the treatment they actually received. 	
 PK

4.1. Protocol Deviations

- Important protocol deviations (including deviations related to study inclusion/exclusion criteria, conduct of the trial, patient management or patient assessment) will be summarised and listed.
- Protocol deviations will be tracked by the study team throughout the conduct of the study in accordance with the Protocol Deviation Management Plan.
 - Data will be reviewed prior to freezing the database to ensure all important deviations and deviations which may lead to exclusion from the analysis are captured and categorised on the protocol deviations dataset.
 - This dataset will be the basis for the summaries and listings of protocol deviations.
- A separate listing of all inclusion/exclusion criteria deviations will also be provided. This will be based on data as recorded on the inclusion/exclusion page of the eCRF.

5. CONSIDERATIONS FOR DATA ANALYSES AND DATA HANDLING CONVENTIONS

Table 1 provides an overview of appendices within the RAP for outlining general considerations for data analyses and data handling conventions.

Table 1 Overview of Appendices

Section	Component
10.1	Appendix 1: Protocol Deviation Management
10.2	Appendix 2: Time & Events
10.3	Appendix 3: Treatment States and Phases
10.4	Appendix 4: Data Display Standards & Handling Conventions
10.5	Appendix 5: Derived and Transformed Data
10.6	Appendix 6: Premature Withdrawals & Handling of Missing Data
10.7	Appendix 7: Values of Potential Clinical Importance

6. STUDY POPULATION ANALYSES

6.1. Overview of Planned Analyses

The study population analyses will be based on the Safety Population, unless otherwise specified. These analyses will be performed in each part.

Table 2 provides an overview of the planned study population analyses, with full details of data displays being presented in Appendix 9: List of Data Displays.

Table 2 Overview of Planned Study Population Analyses

Display Type	Data Displays Generated		
	Table	Figure	Listing
Subject Disposition			
Subject Disposition and Reason for Study Withdrawal	Y		Y
Screening Status and Reasons for Screen Failure	Y		Y
Subjects for Whom the Treatment Blind was Broken			Y
Planned and Actual Treatments			Y
Protocol Deviations			
Important Protocol Deviations	Y		Y
Inclusion/Exclusion Criteria Deviations			Y
Populations Analysed			
Study Populations	Y		
Subjects Excluded from Any Population			Y
Demographic and Baseline Characteristics			
Demographic Characteristics	Y		Y
Demographic Characteristics for Screening Failure			Y
Age Ranges	Y		
Race and Racial Combinations	Y		Y
Race and Racial Combinations for Screening Failure			Y
Medical Conditions and Concomitant Medications			
Medical Conditions			Y
Concomitant Medications			Y
Exposure and Treatment Compliance			
Exposure to Study Treatment			Y
Meal			
Meal start and end days/times on fed treatment			Y

NOTES:

- Y = Yes display generated.

7. SAFETY ANALYSES

The safety analyses will be based on the Safety Population, unless otherwise specified. These analyses will be performed in each part.

Adverse events occurred in washout period will be included in adverse events analyses for previous period. Also adverse events occurred in follow up period will be included in safety analyses for the last period.

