5. STUDY DESIGN

5.1. Overall Design

This study consists of two parts;

Part 1

This is a double blind, placebo-controlled, 3-period crossover, ascending dose, single oral administration in the fed condition (high fat meal). During treatment periods 1 to 3, subjects will be randomized and receive the treatments:

- GSK1325756H 10 mg, single dose, in the fed state
- GSK1325756H 50 mg, single dose, in the fed state
- GSK1325756H 100 mg, single dose, in the fed state, or
- Placebo, single dose, in the fed state

Subjects will have a screening visit within 30 days prior to the first dose of study treatment. A minimum washout period of 7 days from the dose of GSK1325756 will be required between each treatment period. Subjects will receive three treatment periods in the study. Subjects will be housed in the Clinical Research Unit from Day -1 (the day before dosing) through Day 3 for Period 1 and 2, from Day -1 (the day before dosing) through Day 4 for Period 3. Subjects will return to the clinic 7 days (at least) after the previous administration day for Period 1 and 2, and subjects will visit the unit on Day 8 (+/- 1 day) of the last dosing for Part 3 for follow-up.

For each dosing period, the progress to the next period will be determined by GSK medical monitor and investigator based on the blinded safety profiles (AE, clinical laboratory values, vital signs and 12-lead ECG). Furthermore, for the progresses Period 2 to Period 3, GSK medical monitor will determine the appropriateness of the progresses Period 2 to Period 3 based on the result of blood concentration of GSK1325756 assessed by the sponsor's person who is responsible for confirmation of concentration under unblind.

Table 2 Dose regimen for GSK1325756H or placebo

Group	n	Period 1	Washout	Period 2	Washout	Period 3
A	6	10 mg	at least 7 days	50 mg	at least 7 days	Placebo
B	6	10 mg		Placebo		100 mg
C	6	Placebo		50 mg		100 mg

Part 2

This is an open label, 2-way crossover, single oral dose in the fed (low fat meal) and fasted states.

Subjects will have a screening visit within 30 days prior to the first dose of study treatment, two treatment periods separated by at least 7 days, and follow-up. Subjects will be housed in the Clinical Research Unit from Day -1 (the day before dosing) through Day 3 (for Period 1 and 2), and re-visit 7 (± 1) days after the last dose of Period 2 for follow-up.

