9.1.1. Time Period and Frequency for Collecting AE and SAE Information

- All SAEs will be collected from the signing of the ICF until the follow-up visit at the time points specified in the SoA (Section 2).
- All AEs will be collected from the start of treatment until the follow-up visit at the time points specified in the SoA (Section 2).
- Medical occurrences that begin before the start of study treatment but after obtaining informed consent will be recorded on the Medical History/Current Medical Conditions section of the CRF not the AE section.
- All SAEs will be recorded and reported to the sponsor or designee within 24 hours, as indicated in Appendix 4. The investigator will submit any updated SAE data to the sponsor within 24 hours of it being available.
- Investigators are not obligated to actively seek AEs or SAEs in former study participants. However, if the investigator learns of any SAE, including a death, at any time after a participant has been discharged from the study, and he/she

considers the event to be reasonably related to the study treatment or study participation, the investigator must promptly notify the sponsor.

- The method of recording, evaluating, and assessing causality of AEs and SAEs and the procedures for completing and transmitting SAE reports are provided in Appendix 4.

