10.2. Appendix 2: Time & Events

Part 1, Period 1-2

Day	Screening	Day-1	Day 1												Day 2	Day 3	
Time post-dose			Pre-dose	0 h	0.25 h	0.5 h	0.75 h	1 h	2 h	3 h	4 h	6 h	8 h	10 h	12 h	24 h	48 h
Informed consent	X																
Subject demography /Medical history	X																
Height, Weight, BMI	X																
Urine drug screen	X																
Serological test	X																
Physical examination	X	X	X									X				X	X
Vital signs (PR, BP, temp)	X	X	X									X				X	X
12-lead ECG	X	X	X									X				X	X
Ophthalmic examination	X ³																
SAEs ²	<=====>																
AEs ²	<=====>																
Con Med review	<=====>																
Hematology, clinical chemistry and urinalysis	X	X															X
Administration				X													
PK sampling			X		X	X	X	X	X	X	X	X	X	X	X	X	
Admission			X														
Discharge																	X

1. Screening visit will occur only prior to the first dosing. Treatment Period 2 will occur after at least 7-days wash-out period. High fat meal will be started and completed before within 30 minutes of GSK1325756H/Placebo dosing.
2. All SAEs will be collected from the signing of the ICF until the follow-up visit at the time points specified. All AEs will be collected from the start of treatment until the follow-up visit at the time points specified (see Section 9.1 Adverse Events).
3. Ophthalmic examinations are conducted on the day between Screening and Day-1. However, it is not carried out for those who are ineligible due to other screening criteria.

Part 1, Period 3

Day	Day-1	Day 1												Day 2	Day 3	Day 4	Follow up ^{2,3}		
		Pre-dose	0 h	0.25 h	0.5 h	0.75 h	1 h	2 h	3 h	4 h	6 h	8 h	10 h	12 h	24 h	48 h	60 h	72 h	
Physical examination	X	X								X					X	X		X	X
Vital signs (PR, BP, temp)	X	X								X					X	X		X	X
12-lead ECG	X	X								X					X	X		X	X
Ophthalmic examination																			X
SAEs	<=====>																		
AEs	<=====>																		
Con Med review	<=====>																		
Hematology, clinical chemistry and urinalysis	X																	X	X
Administration			X																
PK sampling		X		X	X	X	X	X	X	X	X	X	X	X	X	X	X	X	
Admission	X																		
Discharge																			X

1. Treatment Period 3 will occur after at least 7-days wash-out period. High fat meal will be started and completed before within 30 minutes of GSK1325756/Placebo dosing.
2. Follow up visit will occur after 7 days (+/- 1day) of the last dosing.

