10.3.2.1. Treatment States for AE Data

Treatment State	Definition
Pre-Treatment	AE Start Date and Time < Dosing Start Date and Time
Part 1: Period 1	Dosing Start Date and Time in Period 1 ≤ AE Start Date and Time < Dosing Start Date and Time in Period 2 (Part 1)
Part 1: Period 2	Dosing Start Date and Time in Period 2 ≤ AE Start Date and Time < Dosing Start Date and Time in Period 3 (Part 1)
Part 1: Period 3	Dosing Start Date and Time in Period 3 ≤ AE Start Date and Time (Part 1)
Part 2: Period 1	Dosing Start Date and Time in Period 1 ≤ AE Start Date and Time < Dosing Start Date and Time in Period 2 (Part 2)
Part 2: Period 2	Dosing Start Date and Time in Period 2 ≤ AE Start Date and Time (Part 2)
Onset Time Since First Dose (Minute)	If Dosing Start Date and Time > AE Onset Date and Time = AE Onset Date and Time – Dosing Start Date and Time If dosing Start Date and Time ≤ AE Onset Date and Time = AE Onset Date and Time - Dosing Start Date and Time +1 Missing otherwise
Onset Time Since Last Dose (Minute)	AE Start Date and Time – Most Recent Treatment Start Date and Time + 1
Duration (Minute)	AE Resolution Date and Time – AE Onset Date and Time + 1
Drug-related	If relationship is marked 'YES' on eCRF

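### In Part 1, AE percentages by dose can give 100 mg less observation time than 10 and 50 mg if washouts run past about 7 days; a table limited to onset within 6 days of dosing would equalise it

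*SAP*

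**What the plan says.** **Attribution.** SAP section 7 has two rules: "Adverse events occurred in washout period will be included in adverse events analyses for previous period" and "Also adverse events occurred in follow up period will be included in safety analyses for the last period". Section 10.3.2.1 turns them into date conditions. A Period 1 event in Part 1 must satisfy "AE Start Date and Time < Dosing Start Date and Time in Period 2 (Part 1"), and Period 2 likewise runs to the Period 3 dosing. Period 3 has only a lower bound: "Dosing Start Date and Time in Period 3 ≤ AE Start Date and Time (Part 1").

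**Length of each window.** Protocol section 5.1 sets a floor on the gap: "A minimum washout period of 7 days from the dose of GSK1325756 will be required between each treatment period". No ceiling is given in either document. The end of the Period 3 window comes from the Protocol's collection rule in section 9.1.1, "All AEs will be collected from the start of treatment until the follow-up visit", together with the visit timing in SAP section 10.2: "Follow up visit will occur after 7 days (+/- 1day) of the last dosing".

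**Gate before Period 3.** Protocol section 5.1 requires a blinded safety review before each next period. Before Period 3 it adds: "GSK medical monitor will determine the appropriateness of the progresses Period 2 to Period 3 based on the result of blood concentration of GSK1325756".

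**Display.** Part 1 AE Tables 2.1 to 2.4 (SAP section 10.9.5) show numbers and percentages of participants by treatment. No fixed post-dose window, exposure-time adjustment or by-period AE table is listed. Protocol section 10.3.1 makes the safety analysis descriptive.

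**The concern.** Because each active dose belongs to one period, any difference in AE window between periods is a difference between doses, and randomisation to sequence cannot balance it. The top dose is the one whose window is capped. A longer gap after Period 1 or 2 adds days on which events unrelated to treatment are counted to 10 or 50 mg, with no matching days for 100 mg.

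Longer gaps are plausible, especially after Period 2. Its last PK sample is at 48 h on Day 3. With a 7-day gap the next dose falls on Day 8 and admission on Day 7. That leaves about four days for assay, unblinded concentration review and the decision to proceed.

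The extra days say little about the drug. Protocol section 5.4 gives a half-life of 11 to 12 hours and calls 7 days sufficient for washout and follow-up; 168 h is 14 to 15 half-lives. AEs by dose address a stated Part 1 objective, so a percentage for 100 mg that is low only because of a shorter window could be misread as good tolerability.

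**Working it through.** **1. Dose by period.** Three sequences of 6 (Protocol Table 2):

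| Treatment | Period 1 | Period 2 | Period 3 | Total |
|---|---|---|---|---|
| 10 mg | 12 | 0 | 0 | 12 |
| 50 mg | 0 | 12 | 0 | 12 |
| 100 mg | 0 | 0 | 12 | 12 |
| Placebo | 6 | 6 | 6 | 18 |

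This reproduces the 12 per active dose in Protocol section 10.1.1. Dose and period are fully confounded for active treatment.

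**2. Windows.** Let G be the dose-to-dose gap (at least 7 days) and F the time to follow-up (7 days, range 6 to 8). The window is G for 10 and 50 mg and F for 100 mg. The ratio G/F at F = 7, with the range for F = 8 to 6, is:
- G = 7: 1.0 (0.88 to 1.17)
- G = 14: 2.0 (1.75 to 2.33)
- G = 21: 3.0 (2.6 to 3.5)

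Pooled placebo at G = 14 and F = 7 averages (6×14 + 6×14 + 6×7)/18 = 11.7 days, so 100 mg against pooled placebo is affected in the same direction.

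**3. Expected incidence with no drug effect.** The documents give no background rate and no actual gap. Assume a constant rate r of 0.5%, 1% or 2% of participants per day. Expected incidence = 1 − exp(−r × days).

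| r per day | 7 days | 14 days | 21 days |
|---|---|---|---|
| 0.5% | 3.4% | 6.8% | 10.0% |
| 1% | 6.8% | 13.1% | 18.9% |
| 2% | 13.1% | 24.4% | 34.3% |

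**4. In participants, out of 12.** For 14 against 7 days at 1% per day: 12 × (13.1% − 6.8%), about 0.75. At 0.5% it is 12 × (6.8% − 3.4%), about 0.4; at 2% it is 12 × (24.4% − 13.1%), about 1.4. For 21 against 7 days at 1%: 12 × (18.9% − 6.8%), about 1.5. One participant is 8.3%.

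**5. What could be masked.** The true added incidence at 100 mg that would leave the table level across doses is q = 1 − exp(−r × (G − F)). For G = 14 and F = 7, q is 3.4%, 6.8% and 13.1% at the three rates.

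**6. With a common 6-day window.** The expected background is the same for every treatment: 3.0%, 5.8% and 11.3% at the three rates.

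**The case against.** The case against giving this much weight is good, and most of it stands.

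- **Size is assumed.** No actual gap, assay turnaround or background rate is documented. At 14 days and 1% per day the effect is under one participant in 12.
- **Safety is descriptive.** No formal comparison is planned, and progression between periods rests on separate reviews, not on these tables. Only the reading of the tables is affected.
- **Other displays help.** Tables 2.3 and 2.4 are restricted to drug-related events, judged by investigators who are blinded in Part 1. They use the same windows but are less exposed to background events. SAP section 10.3.2.1 derives onset time since last dose, and the AE listing shell (AE9CP) shows it. With 18 participants a recount by hand is feasible, though no planned table makes one.
- **The direction is not certain.** Period 3 has one more in-house day and 72 h assessments. The only post-dose ophthalmic examination in Part 1 is at its follow-up, where 12 of 18 participants last received 100 mg. These push recorded events towards 100 mg. The extra washout days are outpatient days, and equal daily AE capture on them is assumed.

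A reader might infer that the planned tables will hide or reverse a dose trend. The documents do not support that: they allow unequal windows but do not show that these will occur. A reader might also extend the point to Part 2. There, sequences D and E balance fed and fasted over the two periods, so window length is not tied to treatment.

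**Conclusion.** The point holds as a conditional one for Part 1. The plan permits AE observation time to differ by dose, and the Part 1 AE tables do not correct for it. If washouts run longer than about 7 days, 10 and 50 mg, and pooled placebo on average, are observed longer than 100 mg, and a rise at 100 mg can be understated. With 7-day gaps and follow-up on day 7 the bias is nil; the one-day tolerance on follow-up alone moves the 100 mg expectation only between 5.8% and 7.7% at 1% per day, against 6.8% for the lower doses.

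The sizes above rest on assumed gaps and a constant assumed background rate. Over the ranges shown for 14-day gaps, the effect is about 0.4 to 1.4 participants in 12. That does not undermine the study, but it is enough to blur a comparison between groups of 12 and is cheap to remove.

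**What to change.** For Part 1 only, add to SAP sections 7 and 10.3.2.1 an all-AE table by treatment restricted to onset within 6 days of dosing, and name it as the table for comparisons between doses. Six days is the shortest permitted follow-up and therefore the longest window observed after every completed dose. An 8-day limit would not equalise the windows, because follow-up may fall on day 6 and the next dose on day 7.

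Keep the existing dosing-to-dosing tables and the AE listing with time since last dose, so no event is lost. AE collection, the washout and the visit schedule do not change, and Part 2 needs no change.

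The cost is one date condition on data already collected, one extra table and its entry in SAP section 10.9.5. The new table leaves out events that start after day 6, which remain in the existing displays. It equalises observation time but does not remove the confounding of dose with period.
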